6.1 DETERMINATION OF SAMPLE SIZE

This study is open to all patients who completed FHTR2163 treatment and follow-up through the final (Week 76) visit of the parent study and meet the eligibility criteria outlined in Sections 4.1.1 and 4.1.2). Accordingly, the sample size for this study is not based on a formal sample size calculation.

6.2 SUMMARIES OF CONDUCT OF STUDY

The clinical database will be used to assess study conduct. The numbers of patients who enroll, discontinue, or complete the study will be summarized. Reasons for premature study treatment discontinuation and study discontinuation will be listed and summarized. Patient exposure to study drug (number of study treatments and duration of treatment) will be summarized for all patients and by treatment group. Eligibility criteria deviation and other major protocol deviations will be listed and evaluated for their potential effects on the interpretation of study results.

6.3 SUMMARIES OF DEMOGRAPHIC AND BASELINE CHARACTERISTICS

Demographic data, OLE baseline safety data (e.g., vital signs and laboratory test results), and OLE baseline disease characteristics (e.g., GA area, BCVA, annualized GA growth rate) will be summarized for all patients and by treatment group through use of descriptive statistics.

6.4 SAFETY ANALYSES

The safety analysis population will consist of all patients enrolled in this study who received at least one dose of study drug.

Safety will be assessed through descriptive summaries of adverse events, ocular assessments (e.g., inflammation, IOP, BCVA), clinical laboratory evaluations, ocular imaging, and immunogenicity against FHTR2163.

Verbatim descriptions of adverse events will be summarized by mapped term, appropriate thesaurus level, and toxicity grade (severity) if applicable (see Section 5.3.3).

6.5 PHARMACOKINETIC ANALYSES

The PK analysis population will consist of all patients enrolled in this study who have at least one FHTR2163 serum or aqueous humor sample. Serum and aqueous humor concentrations of FHTR2163 will be summarized descriptively by treatment arm (with patients grouped according to treatment actually received) and/or by treatment regimen (Q4W or Q8W).

Concentrations of FHTR2163 in serum and aqueous humor may be pooled and analyzed with data from other studies as appropriate.

6.6 IMMUNOGENICITY ANALYSES

The immunogenicity analysis population will consist of all patients enrolled in this study who have at least one serum ADA assessment. The numbers and proportions of ADA-positive patients and ADA-negative patients at baseline (baseline prevalence) as well as after drug administration (postbaseline incidence) will be summarized by treatment arm (with patients grouped according to treatment actually received) and/or by treatment regimen (Q4W or Q8W).

The relationship between serum ADA status and safety and PK endpoints may be analyzed and reported via descriptive statistics.

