PROTOCOL

TITLE:	A MULTICENTER, OPEN-LABEL EXTENSION STUDY TO EVALUATE THE LONG-TERM SAFETY AND TOLERABILITY OF INTRAVITREAL INJECTIONS OF FHTR2163 IN PATIENTS WITH GEOGRAPHIC ATROPHY SECONDARY TO AGE-RELATED MACULAR DEGENERATION
PROTOCOL NUMBER:	GR42558
VERSION NUMBER:	4
EUDRACT NUMBER:	Not applicable
IND NUMBER:	134632
NCT NUMBER:	NCT04507148
TEST PRODUCT:	FHTR2163 (RO7171009)
MEDICAL MONITOR:	, M.D., Ph.D .
SPONSOR:	Genentech, Inc.
DATE FINAL:	See electronic date stamp below

PROTOCOL AMENDMENT APPROVAL

Date and Time (UTC) 22-Sep-2021 25:09:07

Title Company Signatory **Approver's Name**

CONFIDENTIAL

The information contained in this document, especially any unpublished data, is the property of Genentech, Inc. (or under its control) and therefore is provided to you in confidence as an investigator, potential investigator, or consultant, for review by you, your staff, and an applicable Ethics Committee or Institutional Review Board. It is understood that this information will not be disclosed to others without written authorization from Genentech except to the extent necessary to obtain informed consent from persons to whom the drug may be administered.

FHTR2163—Genentech, Inc. Protocol GR42558, Version 4

PROTOCO	DL HISTORY
---------	-------------------

Version	Date Final
1	15 July 2020
2	10 October 2020
3	3 May 2021

PROTOCOL AMENDMENT, VERSION 4: RATIONALE

Protocol GR42558 has been amended primarily to include two additional treatment arms to provide safety, tolerability, pharmacokinetic, pharmacodynamic biomarker, and immunogenicity data for intravitreal administration of FHTR2163 at 10 mg.

- Two new treatment arms have been added to the study design; patients assigned to these arms will receive either 10 mg of FHTR2163 every 4 weeks (Q4W) or 10 mg of FHTR2163 every 8 weeks (Q8W), respectively. Upon implementation of protocol Version 4, newly enrolling patients from the sham control arms of parent study GR40973 (hereafter referred to as the parent study) will be assigned to the new 10 mg treatment arm that corresponds to the dosing frequency of each patient's original dosing schedule in the parent study (i.e., Q4W or Q8W). No changes will be made to the dosing regimens of patients currently enrolled in Study GR42558 (Sections 3.1, 3.4.1, 4.3.2, 6.2, 6.3, 6.5, and 6.6; Figure 1).

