- Given that the changes in the study design could potentially unmask the parent study, an Internal Monitoring Committee has been added to monitor safety and study conduct during the masked period of the current study, which extends until database lock of the parent study (Sections 3.2, 4.2.2, and 5.1).
- Additional aqueous humor sample collections have been added at Week 24 and Week 72 to assess if sufficient HtrA1 target inhibition is achieved at the 10 mg of FHTR2163 dose level, and additional serum pharmacokinetic (PK) and anti-drug antibody samples have been added at Week 24 and Week 72 to enable assessment of immunogenicity at the 10 mg of FHTR2163 dose level. These sample collections have been added for all treatment arms to maintain masking (Appendix 1 and Appendix 2).

Other changes made to the protocol are as follows:

 Language around pre-injection prophylactic paracentesis procedures being performed outside of pre-specified aqueous humor collection visits has been added to the exclusion criteria, prohibited therapy criteria, and treatment interruption criteria. Specifically, given that such pre-injection prophylactic paracentesis procedures are not pre-specified procedures in the Informed Consent Form and procedure sequelae could confound the interpretation of the study outcomes, pre-injection prophylactic paracentesis procedures have been added as an exclusionary criterion and as a prohibited therapy. Treatment interruption criteria have been amended to indicate that if an enrolled patient is deemed to require a prophylactic paracentesis prior to study treatment administration, study treatment must be interrupted and may be resumed as determined by the investigator with consultation from the Medical Monitor. In addition, permitted therapy criteria have been clarified to allow for post-injection paracentesis as per clinical judgment. Furthermore, treatment interruption criteria have been amended to indicate that if an enrolled patient has had three consecutive post-injection paracentesis procedures performed in the study eye for treatment of adverse events, study drug must be interrupted. Study treatment may be resumed as determined by the investigator with consultation from the Medical Monitor (Sections 4.1.2, 4.4.1, 4.4.2, and 5.1.5; Table 1).

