3.1 DESCRIPTION OF THE STUDY

Study GR42558 is a multicenter, OLE study to evaluate the long-term safety and tolerability of ITV injections of FHTR2163 in patients with GA who completed the parent study. Patients who discontinued from the parent study or discontinued from study treatment prior to completion of the final (Week 76) visit are not eligible for enrollment in this OLE study. Approximately 360 patients are expected to participate in the OLE study.

Patients who consent to participate in the OLE study will be screened for eligibility upon completion of the parent study (i.e., Week 76 visit). The Week 76 visit will serve as the final visit for the parent study and the first (Day 1) visit for the OLE study (i.e., the two visits are to be conducted on the same day), and all Week 76 assessments must be completed prior to conducting Day 1 assessments. If all assessments for the Day 1 visit cannot be completed on the same day as the Week 76 visit, patients may return to the clinic within 28 days to complete the Day 1 visit. If a patient is not able to complete the Day 1 visit within 28 days, the investigator must contact the Medical Monitor for further discussion prior to scheduling the Day 1 visit.

Patients will receive 20 mg of FHTR2163 or 10 mg of FHTR2163 by ITV injection in the same eye selected for injections in the parent study (referred to as the "study eye") Q4W or Q8W for approximately 144 weeks. Dosing frequency will remain consistent with each patient's original dosing schedule in the parent study (i.e., Q4W or Q8W). Upon implementation of protocol Version 4, all eligible patients in the sham control arms of the parent study that are newly enrolling in the OLE study will receive 10 mg of FHTR2163 (Q4W or Q8W; see Figure 1). Patients currently enrolled in the OLE study (i.e. enrolled prior to implementation of protocol Version 4) will continue receiving their current dosing regimen for the remainder of the study.

Figure 1 presents an overview of the study design. Schedules of activities are provided in Appendix 1 and Appendix 2.

FHTR2163—Genentech, Inc. 23/Protocol GR42558, Version 4

Figure 1 Study Schema

Q4W = every 4 weeks; Q8W = every 8 weeks.

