Plasma sample for biomarkers	Ex													х												х	X f	х
Serum ADA sample ^j	Ex							x						х						x						х	X ^{f, j}	х
Serum PK sample for drug concentration ^{j, n}	Ex							x						x						x						x	X ^{f, j}	x
BCVA testing (starting at 4 m) ^k	Ex		x	x	x	x	x	х	x	x	x	x	x	x	x	x	x	x	x	x	x	x	x	x	x	x	х	x

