Appendix 1: Schedule of Activities for Q4W Arms

Day 1–Week 96

- ^j In case of Grade > 0 non-infectious intraocular inflammation, contact the Medical Monitor to discuss case. An additional serum ADA and PK sample should be collected as close as possible to the time of diagnosis. Consider performing CFP/FA (Appendix 12; widefield CFP/FA or standard CFP/FA with peripheral sweeps is preferred), SD-OCT, and uveitis lab workup as clinically indicated. Additionally, consider treatment with corticosteroids if appropriate, based on the individual patient presentation and comorbidities (e.g., diabetes, systemic hypertension), *and consider referring patient to a uveitis specialist and/or rheumatologist, per clinical judgment*.
- ^k Perform assessment prior to dilating the eyes.
- ¹ Perform slit-lamp examination prior to dilating eyes; for grading scales for anterior chamber flare or cells and vitreous cells, see Appendix 5.
- Aqueous humor sample must be collected from the study eye after pretreatment IOP measurement, but prior to study drug administration. For a detailed description of the anterior chamber paracentesis and aqueous humor sample collection procedures, see Appendix 13 and the laboratory manual.
- ⁿ If the Day 1 visit for the OLE is not performed on the same day as the Week 76 visit for the parent study, and serum PK and aqueous humor samples were not collected on Week 76, these samples should be collected on Day 1 of OLE study.
- Both eyes will be dilated prior to ocular imaging. FAF, SD-OCT, OCT-A (as applicable), NI images, and color fundus photographs will be obtained from both eyes and will be forwarded to the central reading center. If a patient misses a study visit where ocular images were scheduled to be obtained, the images should be obtained at the next scheduled visit.
- ^p OCT-A is mandatory for sites that have the capability.
- ^q All assessments (including a detailed examination to evaluate for signs of intraocular inflammation) and sample collection should be completed prior to study drug administration, except for post-treatment finger counting and IOP measurement.

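### Every 10 mg patient is scheduled for a Week 24 ADA sample, but 20 mg patients already past Week 24 at Version 4 are not, so by-arm ADA incidence can differ through sampling alone

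*Combined protocol and SAP*

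**What the plan says.** The Version 4 amendment rationale states that "additional serum pharmacokinetic (PK) and anti-drug antibody samples have been added at Week 24 and Week 72", with the aim of assessing immunogenicity at 10 mg. It adds: "These sample collections have been added for all treatment arms to maintain masking".

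The 10 mg arms are new in Version 4 and receive "newly enrolling patients from the sham control arms of parent study GR40973". Section 3.1 leaves everyone else as they were: "Patients currently enrolled in the OLE study (i.e. enrolled prior to implementation of protocol Version 4) will continue receiving their current dosing regimen".

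In Appendices 1 and 2 the row "Serum ADA sample" takes baseline from the parent study and then schedules Weeks 24, 48, 72, 96 and 144, plus early termination (ET). Unscheduled samples are taken if clinically indicated. For non-infectious intraocular inflammation above Grade 0, a footnote says: "An additional serum ADA and PK sample should be collected as close as possible to the time of diagnosis".

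Section 6.6 admits any enrolled patient with one ADA assessment, before or after dosing. It summarizes ADA status "after drug administration (postbaseline incidence) will be summarized by treatment arm (with patients grouped according to treatment actually received") and/or by regimen. Section 6.5 is parallel for PK: "Serum and aqueous humor concentrations of FHTR2163 will be summarized descriptively by treatment arm". Neither section mentions common visits, protocol version or number sampled. Section 6.8 allows exploratory safety analyses of interim data.

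**The concern.** If incidence means any positive result after baseline, it depends on how often and how early patients are sampled. Here the sampling calendar is tied to dose. No 10 mg patient can have enrolled before the Week 24 sample existed, whereas a 20 mg patient can have passed Week 24 before it was introduced. Adding the sample for all arms does not recover a visit already gone by.

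The contrast most exposed is former-sham 20 mg against former-sham 10 mg. It is the only dose comparison in patients not previously given FHTR2163. All of the former enrolled before Version 4 and all of the latter after it. Section 6.6 does not name this contrast, but it is the natural one for judging immunogenicity by dose.

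Immunogenicity is part of the safety assessment in Section 6.4. Section 1.3.1 links ocular inflammation in monkeys to systemic ADA. A sampling artefact would make 10 mg look the more immunogenic dose.

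**Working it through.** The plan gives no ADA rate, arm size or enrollment curve, so there is no figure of its own to reproduce. All rates below are assumptions.

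**1. Calendars.** The current schedule is Weeks 24, 48, 72, 96 and 144. Removing the two added visits leaves Weeks 48, 96 and 144 as the earlier calendar. This is inferred, because Versions 1 to 3 are not in the documents. Scheduled post-baseline ADA samples are then:

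- 10 mg: 5
- 20 mg, reaching Week 24 after implementation: 5
- 20 mg, past Week 24 at implementation: 4 (Weeks 48, 72, 96, 144)

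**2. Dates.** Version 1 is dated 15 July 2020 and Version 4 was approved on 22 September 2021, 62.0 weeks later. A patient with Day 1 on or before 7 April 2021 was at or past Week 24 at approval. Since 62.0 < 72, nobody was past Week 72. That sample is at risk only where implementation came 10 or more weeks after approval (62 + 10 = 72).

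**3. Share of pre-Version 4 patients missing Week 24.** Assume uniform enrollment over L = 62.0 − a + b weeks, where a is the lag from Version 1 to first enrollment and b the lag from approval to implementation. The share is (L − 24)/L. Section 5.1.1.1 calls the study ongoing on 26 March 2021, 25.7 weeks before approval, so a is taken as at most 62.0 − 25.7 = 36.3. The 12-week limit on b is assumed.

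| a | b | L | Share |
|---|---|---|---|
| 0 | 12 | 74.0 | 50.0/74.0 = 68% |
| 0 | 0 | 62.0 | 38.0/62.0 = 61% |
| 36.3 | 12 | 37.7 | 13.7/37.7 = 36% |
| 36.3 | 0 | 25.7 | 1.7/25.7 = 7% |

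In the widest case (L = 74), (74 − 72)/74 = 3% miss Week 72.

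**4. Gap between five and four samples if every patient in the comparison group missed Week 24.**

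- *Independent positivity p at each sample:* the gap is [1 − (1 − p)^5] − [1 − (1 − p)^4]. For p = 2%, 5%, 10% and 20% this gives 9.6 v 7.8%, 22.6 v 18.5%, 41.0 v 34.4% and 67.2 v 59.0%. The gaps are 1.8, 4.1, 6.6 and 8.2 points.
- *Simulated onset and duration*, one million patients per scenario, comparing Weeks 24/48/72/96/144 with 48/72/96/144:

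| ADA pattern | Constant onset, 10%/year | 15% of patients with onset in first 24 weeks |
|---|---|---|
| Persistent; no dropout, or 15%/year with ET sample | 0.0 | 0.0 |
| Persistent; 15%/year dropout, no ET sample | 0.3 | 1.0 |
| Transient (mean 12 to 52 weeks); no dropout, or 15%/year with ET sample | 1.3 to 1.9 | 4.0 to 6.0 |

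**5. Scaling.** For all pre-Version 4 patients, multiply by the share in step 3. The same applies to former-sham 20 mg patients if they enrolled in the same pattern. Constant-onset transient ADA gives 0.07 × 1.3 = 0.1 to 0.68 × 1.9 = 1.3 points. Early-onset transient ADA gives 0.07 × 4.0 = 0.3 to 0.68 × 6.0 = 4.1 points. For a whole 20 mg arm, multiply again by the fraction enrolled before Version 4. If that were one half, the 4.1 becomes about 2.

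**6. Denominator.** Patients with only a baseline sample count in Section 6.6. In a table cut at a common study week from 24 up to 48, a 10 mg patient has had one scheduled look and an affected 20 mg patient none, yet both are counted. At a single calendar cut the direction is not fixed. An affected 20 mg patient is short of Week 48 only within 24 weeks of implementation, when 10 mg patients starting at the same implementation date have not reached Week 24 either.

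**7. Shared visits.** On Weeks 48, 72, 96 and 144 each group has four scheduled samples, so the scheduled-sampling difference is zero by construction.

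**The case against.** The strongest reply is that this is a non-randomized study with a descriptive, non-primary ADA summary. The new samples apply to every arm, and later 20 mg enrollees get the full schedule and dilute the imbalance. ET samples and inflammation-triggered samples catch some of what Week 24 would have caught. Section 6.6 does not rule out a by-visit display. The 20 mg patients from the active parent arms have prior exposure, so whole arms are not comparable on ADA anyway.

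Much of this stands, and it limits the size. It does not remove the problem. Later 20 mg enrollees come from the active parent arms, so they do not dilute the former-sham contrast. Triggered samples help only in patients with inflammation. Not excluding a by-visit display is not the same as planning one.

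A reader might also infer that the remedy is a headline incidence confined to Weeks 48, 96 and 144. The documents do not support that. It would discard Week 72, which nearly everyone can still give, along with ET and inflammation-triggered samples. It could also hide ADA in the arm these samples were added to study. If 10% were truly positive and 30% of those only at Week 24, the 10 mg figure would fall to 10% × (1 − 0.30) = 7%.

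**Conclusion.** The point holds as a possibility that the plan leaves uncontrolled: by-arm ADA incidence can be higher at 10 mg through sampling alone. It requires some ADA to be transient, or ET samples to be missing. In the simulated scenarios with transient ADA the gap is 1.3 to 6.0 points per affected patient. It falls to about 0.1 to 4.1 points across pre-Version 4 enrollees and is smaller for a whole 20 mg arm. These sizes rest on assumed onset, duration, dropout, uniform enrollment and the two lags, and on the inferred earlier calendar.

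Three stronger readings are not supported:

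- That incidence must differ. With persistent ADA and ET samples the simulated gap is 0.0.
- That two samples are lost. Generally only Week 24 is.
- That all former-sham 20 mg patients lack Week 24. Those who had not reached it at implementation are scheduled for it, and the affected share could be as low as about 7%.

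The change is worth making because it is cheap and the ADA table will be read by dose.

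**What to change.** In Section 6.6:

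- Keep the all-samples post-baseline incidence, including ET and inflammation-triggered samples. Split the 20 mg row by enrollment before or after Version 4.
- Add a by-dose comparison row that leaves out Week 24 and uses the shared scheduled visits (Weeks 48, 72, 96, 144). Leave out Week 72 as well for any site that implemented Version 4 too late to collect it.
- Require at least one post-baseline ADA sample for the incidence denominator.
- Show ADA results by visit with the number sampled.

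In Section 6.5, give the number sampled beside the Week 24 PK summary for 20 mg, since that summary can include only patients who reached Week 24 after implementation.

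The cost is a few sentences and some extra table rows, with no new samples. The shared-visit row does not count ADA seen only at Week 24, so it should stand beside the all-samples figure and not replace it.

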6.7 BIOMARKER ANALYSES

Mean change in GA area from parent study baseline and OLE study baseline, as measured by FAF imaging and determined by a central reading center, will be summarized by descriptive statistics. The relationship between change in GA area and *HTRA1* risk-variant status (i.e., carriers versus non-carriers of the *HTRA1* AMD risk variant, rs10490924) will be explored. Biomarkers will be analyzed together with PK data to explore PK/PD relationships. Additional analyses will be performed to identify biomarkers that are predictive of response to FHTR2163, are associated with rate of progression to a more severe disease state, are associated with susceptibility to developing adverse events, can provide evidence of FHTR2163 activity, or can increase the knowledge and understanding of disease biology and drug safety.

6.8 INTERIM ANALYSES

No formal interim analysis is planned since all patients will receive active FHTR2163 treatment. Exploratory safety analyses may be performed with interim data (e.g., to support regulatory submissions).

7. DATA COLLECTION AND MANAGEMENT

7.1 DATA QUALITY ASSURANCE

The Sponsor will be responsible for data management of this study, including quality checking of the data. Data entered manually will be collected via EDC through use of eCRFs. Sites will be responsible for data entry into the EDC system. In the event of

FHTR2163—Genentech, Inc. 65/Protocol GR42558, Version 4 discrepant data, the Sponsor will request data clarification from the sites, which the sites will resolve electronically in the EDC system. The designated Functional Service Provider will be responsible for discrepancy management.

The Sponsor will produce an EDC Study Specification document that describes the quality checking to be performed on the data. Central laboratory data and ocular imaging will be sent directly to the Sponsor, using the Sponsor's standard procedures to handle and process the electronic transfer of these data.

eCRFs and correction documentation will be maintained in the EDC system's audit trail. System backups for data stored by the Sponsor and records retention for the study data will be consistent with the Sponsor's standard procedures.

The Sponsor will supply eCRF specifications for this study.

